## 1 LIST OF ABBREVIATIONS AND DEFINITION OF TERMS

The following abbreviations of specialist terms are used in this protocol:

Abbreviation	Meaning
AE	Adverse event
COVID-19	Coronavirus disease 2019
CRF	Case report form
FDA	Food and Drug Administration
GCP	Good Clinical Practice
ICF	Informed consent form
ICH	International Council on Harmonization
ID	Identification
IEC	Independent Ethics Committee
IOP	Intraocular pressure
IP	Investigational product
IRB	Institutional Review Board
MedDRA	Medical Dictionary for Regulatory Activities
SAE	Serious adverse event
SAP	Statistical analysis plan
SUSAR	Suspected unexpected serious adverse reaction
VA	Visual acuity

## 2 SYNOPSIS

Protocol Title	A randomized, controlled study to evaluate the safety and effectiveness of treatment with an intracanalicular dexamethasone (0.4mg) insert in the operating room following cataract surgery/intraocular lens implant (IOL) with or without iStent/Hydrus/Goniotomy when placed in the lower punctum compared to the upper punctum.
Phase of Clinical Study	Phase 4, Collaborative Study ✓
Investigational Product	DEXTENZA (dexamethasone ophthalmic insert, 0.4mg) for intracanalicular use
Study Objective	To assess the safety and effectiveness of treatment with an intracanalicular dexamethasone (0.4mg) insert in the operating room following cataract surgery/intraocular lens implant (IOL) with or without iStent/Hydrus/Goniotomy when placed in the lower punctum compared to the upper punctum.
Efficacy and Safety Endpoints	
Primary Efficacy:
 
 
• Absence of anterior chamber cells at Day 14 as measured by Summed Ocular Inflammation Score (0 to 4)
 
• Absence of ocular pain at Day 8 as measured by ocular pain assessment numerical grading scale (0 to 10)
 
 
Secondary Efficacy:
 
 
• Mean change in BCVA from Baseline
 
• Number and percentage of subjects with complete absence of pain
 
• Number and percentage of subjects with complete absence of cell
 
• Measuring cell, pain, and flare on Day 8, 14, 30
 
• Physician ease of insertion and visualization
 
• Number of attempts to successfully insert Dextenza
 
• Dry eye severity as measured by VAS at baseline, Day 8 and Day 30
 
• Record insert retention up to 30 days
 
 
Safety:
 
 
• Adverse events (AEs)
 
• Intraocular pressure (IOP)
 

Number of Sites	Single site, United States (US)

The SPENCER Study

Number of Subjects Planned	Up to 80 eyes; at least 60 eyes
Study Population	Subjects undergoing non-complicated CCI CE/PCIOL in one or both eyes with or without iStent/Hydrus/Goniotomy.

**The SPENCER Study**

	

9. Have a history of herpes simplex virus keratitis or present active bacterial, viral, or fungal keratitis in either eye

10. Have a history of complete punctal occlusion in one or both punctum

11. Currently use topical ophthalmic steroid medications

12. Are unwilling or unable to comply with the study protocol

13. Are determined by the Investigator to not be included for reasons not already specified (e.g., systemic, behavioral, or other ocular disease/abnormality) or if the health of the subject or the validity of the study outcomes may be compromised by the subject's enrollment

Sample Size Considerations	No formal sample size calculations were performed.
Statistical Methods	No formal statistical testing will be done. All data will be descriptive in nature. Summaries for continuous variables will include the sample size, mean, standard deviation, median, minimum, and maximum. Summaries for discrete variables will include frequencies and percentages. Data will be displayed overall, as applicable.

#### 4.2 Rationale for Study Design

Following ophthalmic surgery the current standard of care is to prescribe corticosteroid drops to treat both ocular pain and inflammation. Typically, a dose of topical corticosteroids is prescribed and tapered through the post-operative period, generally 2 to 4 weeks. Patients are expected to administer multiple drops, with differing administration regimens, through the days and weeks following surgery. There are limitations with the standard of care, including: patient noncompliance, difficulty in administration and poor accuracy of drop administration onto the ocular surface resulting in suboptimal doses of drug administered.

The hydrogel platform that allows for DEXTENZA to be a sustained release, dexamethasone delivery system, allows patients to eliminate topical corticosteroid medication which is associated with lack of compliance and difficulty with use. This clinical study will evaluate the safety and effectiveness of treatment with an intracanalicular dexamethasone (0.4mg) insert in the operating room following cataract surgery/intraocular lens implant (IOL) with or without iStent/Hydrus/Goniotomy when placed in the lower punctum compared to the upper punctum.

## 4.3 Risk-Benefit Analysis

### 4.3.1 Benefit

Dextenza has several potential advantages over topical corticosteroid drops given that it requires a single application that is relatively easy to insert using standard dilator and blunt, non-tooth forceps, helps potentially eliminate subject non-compliance with daily drops, delivers therapeutic levels of dexamethasone continuously for the intended duration of therapy, and is free of anti-microbial preservatives.

Dextenza demonstrated a statistically significant improvement over control treatment for both pain and inflammation in double-masked clinical trials. In addition, Dextenza was shown to be generally safe and well-tolerated in studies to date.

### 4.3.2 Risks

The following adverse reactions are typical adverse events that are known to be expected with the insertion procedure using a standard dilator and blunt, non-toothed forceps: eye pain and discomfort, tearing or epiphora (with or without mucopurulent discharge), eye inflammation, allergic reaction, dacrocystitis, canaliculitis, decreased/impaired visual acuity, stenosis (narrowing/closing of the punctum and/or canaliculus), perforation of or trauma to the punctum and/or surrounding tissues, inability to remove test article, need for surgery on the lacrimal system, infection or intraocular infection that if severe could lead to temporary or permanent impairment of eye sight.

Additionally, based on several decades of use of topical ocular corticosteroids, risks have been identified with the use of dexamethasone, some of which have been observed in clinical trials with the DEXTENZA 0.4 mg dexamethasone insert. The following AEs and/or risks have been observed with the administration of corticosteroids: IOP increase/glaucoma/ocular hypertension, masking of infection or enhancing existing infections, delayed healing, cataracts. Other common risks (occurring in  $\geq 1\%$  of safety population) included anterior chamber inflammation, iritis, visual acuity reduced, corneal oedema, cystoid macular oedema, conjunctival hyperemia, eye pain, ocular discomfort, posterior capsule opacification, intraocular pressure increased, and corneal abrasion.

### 4.3.3 Minimization of Risks

With any product, there is always a chance of developing problems from the treatment. However, the risks associated with DEXTENZA have been minimized by formulating the hydrogel intracanalicular insert with constituents that have a long history of safe use in ophthalmic drugs and medical devices. Furthermore, based on the results of DEXTENZA Phase 2 and 3 studies, biocompatibility and preclinical testing, DEXTENZA has been shown to be safe and well tolerated in the eye.

The risks described above will be minimized via selection of experienced and board eligible or board-certified ophthalmologists/optometrists skilled in the use of intracanalicular inserts. All Investigators that will use the investigational product will undergo training per the instructions provided under separate cover. Subjects will be selected and enrolled using clearly defined inclusion and exclusion criteria to ensure that patients with conditions/comorbidities that put them at higher risk for procedural complications are excluded. Treatment and follow up of the subjects will be performed consistent with current medical practices. Furthermore, risks will be minimized by requiring subjects to report for study visits allowing for prospective diagnosis of potential complications. Participants will be given instructions on whom to contact in the event they have any questions or are experiencing any

## **The SPENCER Study**

---

problems. Appropriate therapeutic intervention following standard medical practices will be used in the event of medical complications.

### **4.4 Compliance**

This trial will be conducted in compliance with the protocol, Good Clinical Practice (GCP), including the International Council on Harmonization (ICH) Guidelines, and in general, consistent with the Declaration of Helsinki. In addition, adherence to all applicable local, state, and federal requirements relevant to the use of investigational products is required.

### **4.5 Trial Population**

There will be approximately up to 80 eyes enrolled in this study that are planned to undergo non-complicated CCI CE/PCIOL in one or both eyes with or without iStent/Hydrus/Goniotomy.

## **5 TRIAL OBJECTIVES**

The study objectives are to evaluate the safety and effectiveness of treatment with an intracanalicular dexamethasone (0.4mg) insert in the operating room following cataract surgery/intraocular lens implant (IOL) with or without iStent/Hydrus/Goniotomy when placed in the lower punctum compared to the upper punctum.

## **6 TRIAL DESIGN**

### **6.1 Description of Trial**

This is a randomized, controlled study to evaluate the safety and effectiveness of treatment with an intracanalicular dexamethasone (0.4mg) insert in the operating room following cataract surgery with or without iStent/Hydrus/Goniotomy when placed in the lower punctum compared to the upper punctum.

Each subject's participation is expected to last for approximately 1 month from the DEXTENZA insertion. Visit 1 is the surgical visit; subjects will return for post-operative visits on Day 1, Day 8, Day 14 and Day 30.

### **6.2 Study Endpoints**

#### **6.2.1 Primary Efficacy Endpoint**

- Absence of anterior chamber cells at Day 14 as measured by Summed Ocular Inflammation Score (0 to 4)
- Absence of ocular pain at Day 8 as measured by ocular pain assessment numerical grading scale (0 to 10)

#### **6.2.1.1 Secondary Efficacy Endpoint**

- Mean change in BCVA from Baseline
- Number and percentage of subjects with complete absence of pain
- Number and percentage of subjects with complete absence of cell
- Measuring cell, pain, and flare on Day 8, 14, 30
- Physician ease of insertion and visualization

## **The SPENCER Study**

---

- Number of attempts to successfully insert Dextenza
- Dry eye severity as measured by VAS at baseline, Day 8 and Day 30
- Record insert retention up to 30 days

### **6.2.2 Safety Endpoints**

- Adverse events (AEs)
- Intraocular pressure (IOP)

### **6.3 Randomization and Masking ✓**

This is an open-label study. All subjects will receive DEXTENZA. Subjects will be randomized to one of two treatment groups. Group 1 will receive the insert in the lower punctum on the day of surgery in the OR and Group 2 will receive the insert in the upper punctum on the day of surgery in the OR.

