### Appendix 3    VAS for Eye Dryness

The following procedures should be followed for conducting the study assessments. The Visual Analog Scale (VAS) should be performed prior to all other ocular assessments.

To complete the VAS questionnaire, ask the subject to rate the severity and the frequency of symptom of eye dryness (0%-100%) by placing a vertical mark (|) on the horizontal line to indicate the level of eye discomfort that they are experiencing in both eyes currently (i.e., right now) and how often the eye dryness is experienced.

0% corresponds to: "no discomfort"

100% corresponds to: "maximal (the most) discomfort"

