### **8.4.3 Post-Operative Day 1 (Visit 3, Day 1)**

At the Day after Surgery (Visit 3, Day 1), the following assessments will be performed:

- Prior and concomitant medication
- AEs (record incidence and severity of any adverse events that occur after the insertion)
- Distance visual acuity (VA)
- Ocular pain assessment (0 to 10)
- Slit lamp examination (including anterior chamber count and anterior chamber flare)
- Insert visualization

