### **8.4.4 Post-Operative Day 8 (Visit 4, Day 8) Day 14 (Visit 5, Day 14) and Day 30 (Visit 6, Day 30)**

At the Day 8, Day 14 and Day 30 Visits, the following assessments will be performed:

- Prior and concomitant medication
- AEs (record incidence and severity of any adverse events that occur after the insertion)
- Distance visual acuity (VA)
- Best-Corrected Visual Acuity
- Ocular pain assessment (0 to 10)
- Slit lamp examination (including anterior chamber count and anterior chamber flare)
- Intraocular pressure
- Insert visualization

- MAC OCT Day 30
- Dry eye severity as measured by VAS on Day 8 and Day 30

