## The SITE Study

Insert Visualization		X*		X		X		X		X
Phacoemulsification Time		X								
Indicate the incision type, location, and size (mm)		X								
Prescribe post-op topical therapy regimen		X								
VAS Dry Eye Severity	X			X		X		X		
Physician ease of insertion and visualization		X								
Record number of attempts to successfully insert DEXTENZA		X								

1. Record any medications the subject is taking, as well as those the subject has taken in the previous 60 days prior to Visit 1.
2. Record all adverse events that occur before and after the insertion of the intracanalicular dexamethasone insert in Visit 2 and all adverse events in Visits 3, 4 and 5.
3. To be done in the OR for Group 1 and Group 2
4. To be done after the insert is placed in the OR for Group 1 and Group 2. Visualization will continue to be done at all visits thereafter.
5. Early termination subjects should complete assessments based on the final visit schedule of assessments.

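### No step limits knowledge of the assigned punctum when the two primary outcomes are scored

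*Combined protocol and SAP*

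**What the plan says.** Section 6.3 carries masking in its title, but its content on that subject is "This is an open-label study. All subjects will receive DEXTENZA". The arms differ only in placement: "Group 1 will receive the insert in the lower punctum on the day of surgery in the OR and Group 2 will receive" the same insert in the upper punctum.

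Section 6.2.1 gives two primary endpoints: "Absence of anterior chamber cells at Day 14 as measured by Summed Ocular Inflammation Score (0 to 4") and "Absence of ocular pain at Day 8 as measured by ocular pain assessment numerical grading scale (0 to 10").

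The Day 8, Day 14 and Day 30 visits (Section 8.4.4) include "Slit lamp examination (including anterior chamber count and anterior chamber flare"), and insert visualization appears further down the same bullet list. Section 8.4.3 also lists "Insert visualization" at Day 1. A footnote to the Appendix 1 table adds: "Visualization will continue to be done at all visits thereafter". The one rule on sequence is in Appendix 3, where the dry-eye VAS "should be performed prior to all other ocular assessments".

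Section 4.3.3 has investigators using the product, and Section 12.1 has investigators scoring ophthalmic observations. The two roles are not separated. No section names who grades cells at Day 14 or who rates pain at Day 8.

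**The concern.** The objective in Section 5 is comparative: lower against upper punctum. Both primary endpoints depend on the line between zero and the lowest positive score, which is where judgement counts most. Cells are graded by eye at the slit lamp. Pain is presumably rated by the subject, although the text does not say so.

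If the person giving the score knows which punctum was used and has a view about it, the score can drift in one arm. Such a view is plausible, because Section 10.7 has investigators rate insertion as easier, the same or more difficult. Enrolling more eyes does not reduce a bias of this kind. Since the analysis is descriptive, what is at stake is the observed difference between the groups. There is no type I error rate or power to damage.

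**Working it through.** The plan gives no expected success rate, effect size or sample-size calculation (Sections 10.2 and 10.3), so it has no figure to reproduce. Two checks were made.

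**1. What ordering within a visit can and cannot do**

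- Insert visualization is scheduled on Day 0 (Section 8.4.2), Day 1 (Section 8.4.3), and Days 8, 14 and 30 (Section 8.4.4).
- Visualizations before the Day 8 visit: Days 0 and 1, so 2.
- Visualizations before the Day 14 visit: Days 0, 1 and 8, so 3.
- Sections 8.4.3 and 8.4.4 already list pain, then slit lamp, then visualization. The lists are unordered bullets, so nothing makes that sequence binding.
- A binding order stops the grader from looking at the insert immediately before grading cells. It does not erase what the same examiner saw on Days 0, 1 or 8.
- Order does nothing for pain if the subject already knows the punctum. Only withholding that information could help.
- The VAS is due on Day 8, the primary pain visit, and Appendix 3 puts it first. Any new order must therefore place pain after the VAS at that visit.

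**2. Illustrative size**

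Inputs from the documents: up to 80 eyes and at least 60 (Synopsis). That is 40 or 30 per arm if allocation is equal; Section 6.3 does not state the ratio. Assumptions: success rate p, flip rate, no true difference, and independent eyes.

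Standard error of the difference, sqrt(2p(1 − p)/n), at p = 60%:

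- n = 40: sqrt(2 × 0.6 × 0.4 / 40) = sqrt(0.012) = 11.0 points
- n = 30: sqrt(2 × 0.6 × 0.4 / 30) = sqrt(0.016) = 12.6 points

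If 5 to 10% of all eyes in one arm cross the zero boundary, the difference moves by 5 to 10 points. That is 2 to 4 eyes of 40.

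- n = 40: 5/11.0 = 0.45 to 10/11.0 = 0.91 standard errors
- n = 30: 5/12.6 = 0.40 to 10/12.6 = 0.79 standard errors

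A second parameterisation shows how far this depends on the assumptions. If a fraction m of the not-clear eyes in one arm is graded clear, the false difference is m(1 − p):

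| p | m = 5% | m = 10% | m = 20% |
|---|---|---|---|
| 30% | 3.5 | 7.0 | 14.0 |
| 50% | 2.5 | 5.0 | 10.0 |
| 70% | 1.5 | 3.0 | 6.0 |

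Entries are percentage points, so the range is 1.5 to 14. At p = 60%, the 5 to 10 point shift above needs m = 0.05/0.40 = 12.5% to 0.10/0.40 = 25% of not-clear eyes to be regraded. The upper end is therefore a fairly strong assumption.

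For scale, one regraded eye moves an arm by 1/40 = 2.5 points or 1/30 = 3.3 points. Over p = 30 to 70%, the 95% half-width of a difference is about 20 to 22 points at 40 per arm and 23 to 25 at 30 per arm.

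**The case against.** The strongest case against the point has four parts.

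- **Open label is a disclosed choice in a descriptive study.** This is true, and it limits the weight of the point. The objective is still a comparison between puncta, and a descriptive difference can be biased as easily as a tested one.
- **Both arms get the same insert, and the documents state no expectation favouring either punctum.** This stands. Differential bias is less obvious here than in a trial of active treatment against control, and its direction cannot be predicted.
- **Section 10.6 summarises cells and pain by mean, standard deviation and median, so the result does not rest only on zero against the lowest grade.** This is correct for that summary. However, the endpoints are defined as absence, and Section 10.7 reports numbers and percentages with complete absence.
- **Reordering cannot mask a grader who has already seen the insert.** This also stands. A reader might infer that grading cells before visualization, with one examiner doing every step, would mask the outcome at no staffing cost. The documents do not support that: three scheduled visualizations precede the Day 14 grading, and the listed sequence already has the slit lamp first. Full masking needs a grader who took no part in insertion or earlier visualization. The documents do not show whether this single site has one.

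What remains is partial protection. Recalling one of two puncta from an earlier visit, across up to 80 eyes, differs from seeing the insert just before giving the grade.

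**Conclusion.** The point holds in a limited form. The study is open-label, and no section limits knowledge of the assigned punctum when either primary outcome is scored. A reader might go further and take it as stated that the scorers know the arm. The documents do not say so, because they do not name the scorers and the consent pages are not available to show what subjects are told. Knowledge of the arm is a fair inference from open-label status and from the unseparated investigator role.

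The illustrative effect is 5 to 10 points on the between-group difference, which is a little under half to about nine tenths of a standard error at 40 per arm. It rests on an assumed one-arm flip rate and an assumed 60% success rate. The standard error also assumes equal allocation and independent eyes, although Section 7.1 admits subjects having surgery in both eyes. No evidence in the documents shows that bias of this size, or in either direction, will occur. The change is worth making because most of it costs only wording and it concerns both primary outcomes.

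**What to change.** In Sections 6.3, 8.4.3 and 8.4.4:

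1. State that the subject is not told which punctum was used.
2. Keep the assignment and any earlier visualization findings off the post-operative grading worksheet.
3. Make the order binding: dry-eye VAS where scheduled (to respect Appendix 3), then pain score, then cells and flare graded and entered, then lids and puncta, with insert visualization last.
4. Where existing staffing allows, have cells graded by someone who took no part in insertion or earlier visualization. Otherwise, record on the CRF whether the grader knew the punctum, and report detection bias as a limitation.

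Items 1 to 3 cost protocol wording and CRF page order, and need no extra staff. Item 4 uses a separate grader only if one is already available; the fallback is one CRF field and a sentence in the report. No treatment or visit changes.

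The limit should be stated openly. These steps reduce unmasking but do not ensure masking: visualization on Days 0, 1 and 8 comes before the Day 14 grading, a surgeon or repeat examiner may remember the eye, and a subject may notice the insert.

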### **6.4 Trial Treatment**

DEXTENZA (0.4 mg dexamethasone) will be administered into the canaliculus of the eye. The intracanalicular dexamethasone insert contains 0.4 mg dexamethasone and is designed to provide a sustained and tapered release of therapeutic levels of dexamethasone to the ocular surface for up to 30 days for the reduction of post-operative inflammation and pain associated with ocular surgery. Dexamethasone is an anti-inflammatory 9-fluoro-glucocorticoid (also termed a glucocorticoid agonist) and is the active ingredient found in MAXIDEX® 0.1% (dexamethasone ophthalmic suspension), which contains approximately 50 µg of dexamethasone per drop.

Insertion instructions will be provided under separate cover.

### **6.5 Trial Duration**

Each subject's participation is expected to last for approximately 1 month from the DEXTENZA insertion.

### **6.6 Trial Material Handling and Accountability**

The trial material used in this study is DEXTENZA (0.4 mg dexamethasone).

The trial material will be provided by Ocular Therapeutix, Inc. or its designee, and will be supplied in a sealed foil pouch containing one single DEXTENZA insert.

The trial material will be shipped to the site via overnight shipping using cold packs to maintain a temperature of 2° to 8°C. The Investigator or an approved representative (e.g., pharmacist) will ensure that the investigational product is stored in a secured area, under recommended storage conditions, and in accordance with applicable regulatory requirements. The shipping box is to be opened and stored immediately at the site in a refrigerator intended for trial material at a temperature of 2° to 8°C.

The trial material must be kept in a safe storage area with limited access (e.g., in a refrigerator in a locked/limited access area). The refrigerator should be temperature monitored. The trial material should be stored at controlled refrigerated temperatures from 2°C to 8°C. When the trial material is removed from the refrigerator, it should be visually inspected. Exposure of the trial material to temperatures outside these limits is not recommended.

The recipient will acknowledge receipt of the trial material indicating shipment content and condition. Damaged supplies may be replaced upon notification to Ocular Therapeutix, Inc. or its designee.

